#### STATEMENT OF COMPLIANCE

The study will be conducted in accordance with the International Conference on Harmonisation guidelines for Good Clinical Practice (ICH E6), the Code of Federal Regulations on the Protection of Human Subjects (45 CFR Part 46), and the NIDCR Clinical Terms of Award. All personnel involved in the conduct of this study have completed human subjects protection training.

This protocol is modeled in part based on NIDCR Clinical Trial (Interventional) Protocol Template v4.0 - 20140103

ii

## List of Abbreviations and Acronyms

[figure not shown]
Abbreviation and Acronyms	Name
BLTR	Bilamellar Tarsal Rotation
BRAP	Bevel/rotate/advance procedure
CHW	Community Health Worker
DSMC	Data Safety and Monitoring Committee
ECA	Eyelid Contour Abnormality
FMHACA	Food Medicine and Health Care Administration and Control
	Authority
FTP	File Transfer Protocol (method for securely transferring data
	electronically)
IRB	Institutional Review Board
JHU	John Hopkins University
MTSS	Maximizing Trichiasis Surgery Success (clinical trial)
MTSS-PTT	Maximizing Trichiasis Surgery Success – Post-operative
	Trachomatous Trichiasis (clinical trial)
NEI	National Eye Institute
NIH	National Institutes of Health
PTT	Post-operative Trachomatous Trichiasis
SNNPR	Southern Nations Nationalities and Peoples Region
TT	Trachomatous Trichiasis
UNC	University of North Carolina
WHO	World Health Organization

## PROTOCOL SUMMARY

Title:	Randomized Control Trial of Repeat Surgery for Patients with Post- Operative Trichiasis				
Précis:	In this trial we will randomize 936 individuals with post- operative trichiasis on a 1:1 basis to standard Trabut surgery or the recently developed bevel/rotate/advance procedure (BRAP). Participants will receive trichiasis surgery and will be followed at 1 day, 2 weeks, 3-6 months and 12 months after surgery. The primary outcome is development of post- operative trachomatous trichiasis (PTT) within 12 months after surgery. Logistic regression analyses will be performed to compare the rates of PTT between the two procedures, controlling for demographic characteristics and pre-operative trichiasis severity.				
Objectives:	Primary objective:				
	
 
To determine whether the rate of post-operative trichiasis (PTT) differs significantly at 12 months after repeat surgery with the Trabut procedure compared to surgery with a recently developed procedure, the bevel/rotate/advance procedure (BRAP).
 
				
	Secondary objectives:				
	
 
To determine whether the frequency of moderate/severe eyelid contour abnormalities 12 months after surgery differs between the two procedures.
 
To determine whether the frequency of pyogenic granulomas within 12 months after surgery differs between the two procedures.
 
To determine whether the frequency of PTT differs between the two procedures at 3-6 months after surgery.
 
				
Endpoints	The primary endpoint for this study is presence of one or more eyelashes touching the globe or signs of epilation after repeat trichiasis surgery.				
Population:	Participants will be recruited from three regions in Ethiopia: Southern Nations Nationalities and Peoples Regional State (SNNPR), Oromia, and Amhara. Some participants will be				

	recruited from within the US National Eye Institute (NEI) funded clinical trial of incident trichiasis surgeries, the Maximizing Trichiasis Surgery Success (MTSS) Trial, currently taking place in SNNPR. Other non MTSS post-operative trichiasis (PTT) cases from the 3 regions will also be recruited. All individuals with PTT in at least one eye, aged >18 years, and living in the area will be eligible to participate. We aim to enroll 936 individuals during the 2019-2020 surgical campaigns being supervised by Orbis International, The Carter Center and the Fred Hollows Foundation.
Description of Sites/Facilities Enrolling Participants:	Recruitment will take place at rural health centers and health posts in the SNNPR, Amhara, and Oromia Regions of Ethiopia.
Description of Intervention:	A new surgical procedure, the bevel/rotate/advance procedure (BRAP), for the correction of post-operative trichiasis (PTT) will be compared against Trabut surgery (posterior lamellar tarsal rotation)
Study Duration:	1.5 years
Subject Participation Duration:	12 months
Estimated Time to Complete Enrollment:	Recruitment is scheduled for April 2019 through December 2020.

#### **STUDY DESIGN SCHEMATIC:**

## 1.1 Timeline and Feasibility of Adhering to Study Schedule

The study recruitment and follow up schedule is outlined in the table below.

	Year 1 (Sept 2018 – Aug 2019)		Year 2 (Sept 2019 – August 2020)		Year 3 (September 2020-August 2021)			Year 4 (September 2021-August 2022)								
Activity Ethics Applications	Q1 (Sept- Nov) X	Q2 (Dec- Feb) X	Q3 (Mar- May)	Q4 (Ju- Aug)	Q1 (Sep- Nov)	Q2 (Dec- Feb)	Q3 (Mar- May)	Q4 (Jun- Aug)	Q1 (Sep- Nov)	Q2 (Dec- Feb)	Q3 (Mar- May)	Q4 (Jun- Aug)	Q1 (Sep- Nov)	Q2 (Dec- Feb)	Q3 (Mar- May)	Q4 (Jun- Aug)
Case identification	X	Х	Х	Х	Х	Х	Х		Х	Х						
Randomization, Surgery, 1-day follow up visits			х	x	х	x	х		x	x						
2-week follow up visits			Х	Х	Х	Х	Х		Х	Х						
3-6-month follow up visits				х	Х	х	Х	х	Х	х	Х	х				
12-month follow up visits						х	Х	Х	х	х	Х		х	Х		
Data cleaning and analyses					х	х	х	Х	х	х	х	х	х	х	х	х
Dissemination of Study Findings (manuscripts and presentations)									x	x	x	x	x	х	х	x

## 3. INTRODUCTION

## 3.1 MTSS Trial

The Maximizing Trichiasis Surgery Success Trial (MTSS Trial) is an ongoing US National Eye Institute (NEI) clinical trial evaluating 3 methods for performing incident trichiasis surgery in Ethiopia. The study is enrolling roughly 5000 individuals with previously unoperated trichiasis and following them for 1 year. We anticipate that 15-20% of these individuals will develop trichiasis again during the course of the MTSS trial and these will need repeat surgery. We plan to investigate ways to perform repeat surgery.

## 3.2 Background and Rationale

The World Health Organization (WHO) has set 2020 as the year by which programs should eliminate trachoma as a public health problem. Many countries are rapidly scaling up trichiasis surgery programs to meet this goal. Significant progress has been made, yet much remains to be done, and trichiasis surgery will likely be needed for at least another decade. Post-operative trichiasis (PTT), or the presence of trichiasis after surgery, is a problem that plagues most national programs. In some regions, rates of PTT as high as 50% have been reported. However, consensus has not been reached on how these patients should be managed.

Repeat surgical management of these cases is more challenging than primary surgery because of increased scarring resulting from the first round of surgery plus continued disease progression, both of which cause the tarsus to become thicker and more irregular. In most settings where repeat surgery is performed, patients are operated with the same procedure that they received for their initial surgery. Research indicates that second surgeries using currently available procedures have higher rates of poor outcomes than initial surgeries, with over 40% of patients having repeat PTT within 6 months after surgery and 45% experiencing an eyelid contour abnormality (unpublished data).

Recent WHO guidelines indicate that repeat TT surgery should be performed by the most highly skilled health workers available. Furthermore, at the 2017 annual meeting of the Alliance for the Global Elimination of Trachoma by 2020 (GET 2020), significant discussion focused around the need for identifying an appropriate method for management of PTT cases. It has been proposed that a regional training session should be held to train higher cadres of medical staff on how to perform repeat surgery. Before that time, however, it is critical that the best possible method for addressing these cases is determined. To that end, a clinical trial investigating approaches to improving repeat trichiasis surgery outcomes is urgently needed. Here, we propose to conduct a clinical trial comparing a recently developed procedure, the bevel/rotate/advance procedure (BRAP), to the current standard of care used to treat PTT patients.

## Surgical Procedure Comparison

The Trabut procedure is the WHO-recommended standard procedure used for initial trichiasis surgeries and is also widely used for PTT. The bevel/rotate/advance procedure (BRAP) is a procedure developed by [name] and colleagues in Colombia. They worked together to develop the BRAP by combining steps from existing procedures in order to address multiple challenges associated with conducting repeat trichiasis surgery utilizing current TT surgical procedures. Specifically, in the typical upper eyelid with PTT, the tarsus is thick and scarred, especially near the previous incision. Additionally, the tarsus thickness can be quite variable across the width of the eyelid. These factors make a repeat Trabut or Bilamellar Tarsal Rotation (BLTR) procedure more challenging to perform successfully because it is more difficult to make a uniform incision across these eyelids and the variability of the thickness makes it challenging to stably rotate the inturned eyelashes.

To address these challenges, BRAP employs a beveled full-thickness incision at a location, slightly different from the incision of the original surgery, and utilizes a different approach for repositioning the inturned eyelashes. BRAP was first evaluated in Mitu, Colombia (see letter from Columbian MOH). Then, following training by [name], Ethiopian surgeons performed BRAP procedures in SNNPR, Ethiopia. Specifically, 23 patients were operated with BRAP. Among these, 31 eyelids were assessed 3-6 months post-surgery. These surgeries were performed through the Orbis program to provide care for these patients, not as part of a research project. Of these eyelids, 16% had PTT, and 84% had no evidence of trichiasis at follow up. Of those with PTT, 2 had central trichiatic eyelashes (1 with 1 lash and 1 had 3 lashes). Comparatively, among 4 evelids operated with Trabut during the same period, only 50% had no evidence of trichiasis at follow up. These initial surgeries suggest that this procedure is likely to have a lower rate of second post-operative trichiasis. We believe this procedure may have more success than currently available TT surgery procedures because of the incision location and orientation and the manner in which the eyelashes are repositioned during the procedure.

## 3.3 Potential Risks and Benefits

## Potential Risks

The risks associated with this study are minimal. Repeat surgery to treat post-operative trichiasis is a standard practice commonly performed in many countries, and all subjects enrolled in this study would be offered repeat surgery regardless of whether they participate in the clinical trial. Theoretically, a newly-developed procedure utilizing a new method for repositioning lashes could ultimately be found to have higher rates of post-operative trichiasis or eyelid contour abnormalities. Preliminary data suggest that this new procedure is not associated with an increased risk of eyelid contour abnormalities or of higher post-operative TT rates. However, it is important to be aware of this possible risk.

#### Potential Benefits

Participants enrolled in this study will not benefit directly from this study. The team will give patients surgery even if they decide not to participate in the study. In the study, we will evaluate patients at 3-6 months and 12 months after surgery. Participants may view this as a benefit.

#### **OBJECTIVES AND ENDPOINTS**

#### 3.4 Study Objectives

This study has one primary objective:

1) To determine whether the rate of post-operative trichiasis (PTT) differs significantly at 12 months after repeat surgery with the Trabut procedure compared to surgery performed with a recently developed procedure, the bevel/rotate/advance procedure (BRAP).

This study has three secondary objectives:

- 1) Determine whether the frequency of moderate/severe eyelid contour abnormalities at 12 months after surgery differs between the two procedures.
- 2) Determine whether the frequency of pyogenic granulomas within 12 months after surgery differs between the two procedures.
- 3) Determine whether the frequency of PTT differs between the two procedures at 3-6 months after surgery.

## 3.5 Study Endpoints

#### Post-operative Trichiasis

We will evaluate post-operative trichiasis at two time points after surgery: 3-6 months and 12 months. A patient examiner standardized against [name] or [name] will perform the assessments. The assessment is made by looking at the eyelid with the eye in primary gaze. Any eyelashes touching the eye with the eye in primary gaze are considered to be trichiatic. Presence of post-operative trichiasis (primary outcome) is defined as 1+ trichiatic eyelashes or evidence of recent epilation. If an eyelid has trichiasis at 2 weeks but not at 3-6 months or 12 months, the eyelid will be considered not to have post-operative trichiasis.

#### Eyelid Contour Abnormalities

We will evaluate eyelid contour abnormalities at each post-operative visit. The examiner will grade the presence of abnormality using the definition provided below in the statistical considerations chapter. Both field and photographic grades will be utilized. The field grade will serve as the primary grade for the primary study analyses; secondary analyses will utilize the photograph grade. Examiners will be standardized at

the start of the 3-6 month visits. For primary analyses, the eyelid contour grade at 12 months will be used.

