## 6.2.1 Masking Procedures

The study subject and the outcomes assessor will be masked to treatment assignment. However, the surgeon will not be masked to the treatment assignment, since s/he must know what procedure to perform.

In order to ensure the outcomes assessor is masked, s/he will not be present at the surgical site, and s/he will not have access to data from the baseline and surgical visit. However, because one procedure involves a full-thickness incision and the other does not, we expect that the outcomes assessor will be able to determine which procedure many of the patients received through visual inspection. Thus, we will use photographs as a backup to verify the outcomes reported, by holding cardstock to cover the skin incision scar in the photographs so that evidence/lack of an incision is not visible.

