## 8. STUDY ASSESSMENT PROCEDURES

#### 8.1 Efficacy Assessment

This section lists the procedures and describes the general approach for data collection.

Ocular Examination: The ocular exam will consist of a detailed evaluation of each eyelid. This information will be collected on the day of surgery. At each follow up study visit, the study eye will be assessed for the presence of *repeat* post-operative trichiasis, eyelid contour abnormality and granuloma.

Visual Acuity: Visual acuity will be assessed monocularly at baseline and will be assessed again at the post-operative 3-6 months and 12 months visits; it will be assessed using an Early Treatment of Diabetic Retinopathy (ETDRS) tumbling "E" chart on a smartphone, using the PEEK acuity app.

Trichiasis Surgery: All participants will receive trichiasis surgery with either the BRAP or Trabut procedure.

Photographs: Photographs will be taken of the full face (headshot) and of each eyelid preoperatively, during surgery, immediately postoperatively, and at each follow up visit.

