## Eyelid Contour Abnormalities:

**Primary analysis** of eyelid contour abnormalities will be based on a dichotomous variable: presence or absence of moderate/severe contour abnormality at the final study

visit (12 months) using the field grade, which will be based on the definitions below. For the purposes of this analysis, mild will be combined with "no abnormality" and moderate and severe will be combined to form the "moderate/severe contour abnormality" group. We will adjust for first procedure performed (Trabut or BRAP) and severity of pre-operative trichiasis.

Abnormality	Definition
Mild	Vertical deviation from the natural contour, 1 mm in height (less than half the pupil height in daylight) and affecting 1/3 of horizontal eyelid length
Moderate	Vertical deviation from the natural contour 1–2 mm in height (about the pupil height in daylight) or affecting 1/3–2/3 of horizontal eyelid length
Severe	Vertical deviation from the natural contour 2 mm in height (more than the pupil height in daylight) or a defect >2/3 of the horizontal eyelid length

(Gower et al. 2012 PLoS Negl Trop Dis 6(6): e1713)

**Secondary analyses** will explore the relationship between procedure and the full range of eyelid contour abnormalities, which will require use of the photographic grade that will be graded centrally.

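### The 12-month contour-abnormality comparison is decided on a field grade that the plan expects often to be unmasked; the planned central photograph grade should be masked to arm and made to decide it

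*Combined protocol and SAP*

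**What the plan says.** Section 3.5 (Eyelid Contour Abnormalities) ranks the two grades: "The field grade will serve as the primary grade for the primary study analyses; secondary analyses will utilize the photograph grade". Section 9.3 (Eyelid Contour Abnormalities) does the same for the dichotomous outcome, moderate or severe against mild or none, at the final "visit (12 months) using the field grade, which will be based on the definitions below". This is secondary objective 1 in section 3.4, and section 9.1 gives it a directional alternative: fewer abnormalities with BRAP.

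Section 6.2.1 first sets the aim: "The study subject and the outcomes assessor will be masked to treatment assignment". It then concedes that one incision is full-thickness and the other is not, so that "we expect that the outcomes assessor will be able to determine which procedure many of the patients received through visual inspection". Its answer is that "we will use photographs as a backup to verify the outcomes reported". In these images a piece of card is to hide the scar, so that a viewer cannot tell whether the skin was cut.

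Section 8.1 supplies the images: "Photographs will be taken of the full face (headshot) and of each eyelid preoperatively, during surgery, immediately postoperatively, and at each follow up visit". Section 9.3 plans a central reading of them, for secondary analyses across all grades of abnormality, "which will require use of the photographic grade that will be graded centrally".

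**The concern.** The grade that settles the comparison comes from the person whose masking the plan itself expects to fail in many patients. The cue is on the eyelid being graded, and it differs by arm.

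The step from mild to moderate in the section 9.3 table is about 1 mm of height or one third of lid length, so borderline lids can fall on either side. If knowledge of the arm moves some of them, the field-grade analysis cannot separate that movement from a surgical effect. Section 3.3 names contour abnormality as a possible risk of the new procedure. Lenient grading of BRAP lids could hide such a risk, and strict grading could invent one.

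The plan already contains most of a remedy, but nothing in it lets the photographs change the conclusion.

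**Working it through.** **1. What each section settles**

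| Question | Where | Answer in the plan |
|---|---|---|
| Which grade decides moderate/severe at 12 months? | 3.5, 9.3 | Field grade |
| Is the field assessor masked? | 6.2.1 | Intended, but recognition expected in many patients; no percentage given |
| Are there photographs of each eyelid at 12 months? | 8.1 | Yes, as at every follow-up visit |
| Is the scar hidden in them? | 6.2.1 | Yes, by cardstock |
| Is there a central photograph grade? | 9.3 | Yes, for secondary analyses over all grades |
| Is the dichotomous model on the photograph grade specified? | 3.5, 9.3 | Not explicitly; 3.5 says only that secondary analyses use that grade |
| Are central graders masked to arm? | none | Not stated |
| What happens if the grades disagree? | none | No rule |
| Why is the field grade preferred? | none | No reason given |

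**2. The plan's own figure.** Sample size and power are stated for trichiasis only. With 35% against 24.5% (a 30% relative reduction), two-sided 5% and 80% power, the two-proportion formula with continuity correction gives 316 per arm, 632 in total. Allowing for 10% loss, 632 / 0.9 = 702.2, so 703, against the 700 stated in section 9.2. The figure reproduces. It is used below only for the number per arm.

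**3. Illustration of the stakes**

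Inputs from the documents:
- Per arm, from section 9.2: 700 × 0.9 / 2 = 315.
- Per arm, from the 936 in the Protocol Summary less the 186 excluded in section 9.2: (936 − 186) × 0.9 / 2 = 337.5.
- Two-sided alpha of 5%.

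Assumptions, not in the documents:
- No true difference between procedures.
- A 20% moderate/severe rate. The only rate given is 45% for any abnormality after second surgery (section 3.2).
- A net grading shift of 1 to 5 percentage points in one arm, up or down.
- One independent eyelid per participant, whereas section 9.3 analyses eyes with GEE.

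Formula: with graded rates a and b, d = |a − b| and p = (a + b)/2,

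s0 = √[2p(1 − p)/n], s1 = √[(a(1 − a) + b(1 − b))/n]

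P(reject) = Φ[(d − 1.96·s0)/s1] + Φ[(−d − 1.96·s0)/s1]

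Example, n = 315, 20% against 15%: p = 0.175, s0 = 0.0303, s1 = 0.0302. The first term is Φ[(0.05 − 0.0593)/0.0302] = Φ(−0.31) = 0.38, and the second is negligible. Result: 38%.

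| Shift in one arm | n = 315: up / down | n = 337.5: up / down |
|---|---|---|
| 1 point | 6% / 6% | 6% / 6% |
| 2 points | 9% / 10% | 10% / 10% |
| 3 points | 15% / 16% | 16% / 17% |
| 5 points | 32% / 38% | 34% / 40% |

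With no shift the rate is 5%. The results depend on the base rate. With n = 337.5 and upward shifts of 3 and 5 points they are 18% and 40% at a 15% base, 14% and 31% at 25%, and about 12% and 25-26% at 45%.

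**4. Plausibility of the larger shifts.** At a 20% base, a net 5-point fall regrades 5/20, a quarter, of that arm's positives. Since recognition is expected in many patients but not all, the share among recognised lids would have to be higher still. The 1- and 2-point rows are equally compatible with the documents.

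**The case against.** The strongest reply is that the sponsor saw the problem and acted on it. Section 3.5 says that photograph grades will be used in secondary analyses, without confining them to another endpoint. An analysis of all grades contains the moderate/severe cut, and section 6.2.1 adds a photograph check. A live examination is a defensible primary measure: examiners are standardised, section 12.1.6.2 requires kappa of at least 0.7 for contour abnormality, and the grades are anchored to millimetres, pupil height and thirds of the lid. No figure for gradability or reliability of the photographs is given.

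Much of this stands, and it rules out three stronger readings.

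- A reader might infer that the comparison has no photographic safeguard at all. Sections 3.5, 6.2.1 and 9.3 say otherwise. What is missing is an explicit dichotomous model, a statement of masking and a rule for disagreement.
- A reader might infer that a better, masked grade already exists. Only the scar is stated to be covered. Nothing says that central graders are masked to arm, or whether lid shape could still reveal the procedure.
- A reader might infer that bias is established and favours BRAP. The documents give neither its size nor its direction.

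The reply does not defeat the point. Kappa measures agreement with a standard grader and does not detect grading that differs by arm. A check that cannot change the conclusion does not protect it. The documents offer no reason for letting the field grade decide.

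**Conclusion.** The concern holds in a limited form. For secondary objective 1 the plan lets a grade decide that it expects often to be unmasked. It leaves the available alternative without an explicit dichotomous model, a statement of masking or a rule for disagreement.

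The range of about 6% to 40% is an illustration of what is at stake, not an estimate of this trial's error rate. It rests on the assumed 20% base rate, the assumed net shifts of 1 to 5 points and independent eyelids. That text finding itself needs no arithmetic.

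A reader might extend the point to the primary endpoint. It concerns the contour grade only and does not affect the primary trichiasis conclusion. Label: cheap improvement.

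**What to change.** In sections 3.5 and 9.3:

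1. State that central graders are masked to arm and grade the scar-covered 12-month photographs.
2. Make that grade primary for the dichotomous moderate/severe GEE model, with the same model on the field grade as a sensitivity analysis.
3. Treat ungradable photographs as missing in the main photograph analysis and report their number by arm. Substitute the field grade only in a sensitivity analysis, so that the unmasked grade does not re-enter the primary variable.

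If the sponsor prefers to keep the field grade as primary, the minimum is to prespecify the same dichotomous GEE model on the masked photograph grade and to base the conclusion on it when the two disagree.

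The cost is plan wording, a masking instruction to the graders and one further model. The photographs and central grading are already planned, and the sample size does not change. The downside is the loss of some eyelids to ungradable photographs.
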